### 9.3 POPULATIONS FOR ANALYSES

Intention-to-treat (ITT) Analysis Dataset (i.e. all randomized participants)

### 9.4 STATISTICAL ANALYSES

#### 9.4.1 GENERAL APPROACH

Not Applicable

#### 9.4.2 ANALYSIS OF THE PRIMARY EFFICACY ENDPOINT(S)

The trial will have coprimary outcomes. The first of these will be percent time-in-serious-hypoglycemia (<54 mg/dl) as described above, which will be recorded as a continuous variable theoretically ranging from 0 (no time spent in serious hypoglycemia) to 100 (all time spent in serious hypoglycemia); the realistic range for this outcome is ~0 to 25, as described below. Data on percent time in hypoglycemia will be downloaded from individual CGM sensors and then pooled across both sensors collected during the intensive CGM phase (month +6 to +7) to compute a single value for “time in serious hypoglycemia” for each patient. The primary analysis will be performed using a multivariable linear regression model where treatment assignment is the primary fixed effect of interest, with age, study site, and time-in-serious-hypoglycemia and time-in-range from the baseline CGM (run-in phase, prior to initiation of study treatment) included as covariates. This approach will be used because adjustment for covariates known to be strongly associated with the outcome increases statistical power; including the baseline measurement as a covariate also provides a safeguard against random imbalances in individual level baseline risk of hypoglycemia (e.g. one arm having patients with more hypoglycemic tendencies than the other arm) introducing a bias in the estimated treatment effect.

The second coprimary outcome will be percent time-in-range (70-180 mg/dl). Likewise, this also will be recorded as a continuous variable theoretically ranging from 0 (no time spent in range) to 100 (all time spent in range). The realistic range for this outcome variable is about 10 to 70, based on pilot data also

described below. Again, data from all CGM sensors collected during the intensive CGM phase (month +6 to +7) will be pooled to compute a single value for “time in range” for each patient. The analytic approach used for this endpoint will mirror the approach used for the time-in-serious-hypoglycemia endpoint: a multivariable linear regression model where treatment assignment is the primary fixed effect of interest, with age, study site, and time-in-range from the baseline CGM (run-in phase, prior to initiation of study treatment) included as covariates.

**Incomplete or missing CGM Sensor Data:** Even though returning a baseline CGM sensor (i.e. the one placed during the run-in phase) is one of the trial eligibility criteria, it is expected that some participants may have incomplete or missing CGM sensor data. For example, a CGM sensor could fall off accidentally before the end of each 14 day sensor wear period. Such sensors may also be lost before study staff have an opportunity to download the glucose data.

If a CGM sensor falls off early, or presents with no data due to a sensor download error, or is accidentally removed less than 9.8 days (70% of 14 days; consistent with international consensus recommendations on the use of CGMs in clinical trials), they may receive a replacement sensor. If a participant is able to successfully wear a sensor for 14 days, but a sensor shuts-off early (e.g. only 6 days of glucose measurement data is captured), they will not have a replacement sensor. Rationale: randomization should balance incomplete sensor data across the two study arms.

In the *primary* analysis, we will include all available sensor data (regardless of the duration of sensor wear or the number of days of glucose measurements) collected while enrolled in the study. In a *sensitivity* analysis, we will include only sensors with at least 70% of data availability during each 14 day wear period (i.e.  $\geq 9.8$  days). In another *sensitivity* analysis, we will impute for missing data. In an exploratory analysis, we will include data from 12-month follow-up replacement sensors that were collected after a participant completed study.

**Lost to follow-up:** If a participant discontinues before any of the follow-up CGM data are recorded (e.g. participant has no recorded CGM data at all during follow-up) they will not contribute data to the primary efficacy analysis. As described above, we are planning the study to have sufficient power with a usable analytic sample of  $n=300$  participants. We propose to recruit  $n=400$  participants, which allows for up to 25% attrition (participants that are lost shortly after randomization, before any CGM data have been collected) while retaining sufficient power to test our primary hypothesis.

In recognition of the fact that in some cases a participant’s discontinuation could represent a negative clinical outcome, we will perform several sensitivity analyses to ensure that we are thorough and transparent in reporting the possible effects that the missingness would have on our primary analysis. The first sensitivity analysis will be multiple imputation analysis, imputing the missing outcome data based on observed baseline data; this approach is preferred to single-imputation (e.g. last observation carried forward or assign-the-worst) as it takes into account residual uncertainty in the missing values. The second sensitivity analysis will be a win-ratio analysis where participants that died during the study are ranked as having the worst possible outcome; participants that discontinued study participation due to an adverse event are ranked as having the second worst outcome value; participants that discontinued with no known adverse event are ranked as having the third worst outcome value; and participants that return complete CGM data during the intensive follow-up period are ranked according to their % time-in-serious-hypoglycemia ( $<54$  mg/dl), with higher scores representing worse outcomes. This approach provides an estimate of which treatment arm led to better overall outcomes while including death, discontinuation, and hypoglycemia into a single composite outcome measure. This will

not be the primary analysis due in part to difficulty interpreting the results and the emphasis on glycemic control as the most important outcome in this therapeutic trial, but it will provide an important check that any observed benefits on a time-in-serious-hypoglycemia outcome or the time-in-range outcome are not offset or explained by greater death or discontinuation in the other treatment arm.

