### 3 OBJECTIVES AND ENDPOINTS

OBJECTIVES	ENDPOINTS	JUSTIFICATION FOR ENDPOINTS
Primary  To determine whether insulin glargine reduces the risk of serious hypoglycemia or improves glycemic Time in Range (TIR) at 6 months when compared against standard of care human insulin (e.g. NPH or premixed 70/30)	The coprimary outcomes for this trial are 1) percent time-in-serious-hypoglycemia (<54 mg/dl) and 2) percent time-in-range (70-180mg/dl).	We selected these coprimary outcomes after consulting international experts and reviewing international consensus guidelines. Even though level 2 hypoglycemic events (i.e. <54mg/dl) are less common than milder, level 1 events (i.e. <70mg/dl), they are far more likely to be clinically significant. Experts also provided feedback that it was important to assess efficacy on both hypoglycemia and time-in-range (increasingly accepted among clinicians as a valid surrogate endpoint by itself since durable increases in TIR are likely strongly associated with good glycemic control and therefore a reduction in the risk of

OBJECTIVES	ENDPOINTS	JUSTIFICATION FOR ENDPOINTS
		microvascular complications of type 1 diabetes), since a benefit on either of these two outcomes will be useful clinical knowledge.
Secondary		
To determine whether insulin glargine improves glycemic control when compared against standard of care human insulin (e.g. NPH or premixed 70/30)	HbA1c (%)	HbA1c is a widely accepted surrogate for glycemic control and currently serve as treatment targets recommended by several professional societies, including the ADA/EASD, ACP and others.

Ascertainment of the Study Outcomes: Patients will be followed from the start of randomization (day 0) up through +12 months. At every 3 months, study participants will return to clinic for routine follow-up (including insulin refills) and HbA1c testing, as is currently the standard of care.

Blinded CGM sensors (duration=14 days each) will be placed on every study participant according to following schedule: (1) One baseline sensor during the run-in phase (i.e. before randomization), (2) one follow-up sensor starting 3 months after randomization, (3) two back-to-back sensors at 6 months after randomization and (4) one sensor at the final 2 weeks of the study (during month 12), to assess durability of CGM results.

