### 8.2 SAFETY AND OTHER ASSESSMENTS

Study Measurements

Baseline demographics/comorbidities	Description
Age	At time of randomization, in years
Duration of type 1 diabetes	Based on self-report or extraction from medical record, in years
Type of insulin regimen	Generally, as two categories, NPH + regular (basal/bolus regimen) or premixed 70/30
Number of units of insulin per day	Total number of international units of insulin used per day, including all basal and bolus insulins.
Mean HbA1c (%) [SD]	HbA1c laboratory result (units=%), most recent
Complications of Type 1 Diabetes	Clinical presence or absence of diabetic retinopathy, neuropathy, or nephropathy (extracted from medical record)

Hypoglycemic events	Number of episodes of symptomatic hypoglycemic events in the past 12 months
Co-Primary Outcomes:	
Time-in-serious hypoglycemia	% spent less than 54mg/dl, averaged across all daily measures averaged across two CGM sensors starting 6 months after randomization
Time-in-range (TIR)	% between 70 and 180mg/dl inclusive, averaged across two CGM sensors 6 months after randomization
Secondary Outcomes:	
Time-in-hypoglycemia	% spent less than 70mg/dl
Time-above-range	% spent greater than 180mg/dl
Nocturnal hypoglycemic events	Number of events (defined as >=15mins in duration < 70mg/dl) between 1200 and 0600
Glycemic control (HbA1c)	Mean HbA1c lab result at baseline, 3, 6, 9 and 12 months after randomization
Rate of severe hypoglycemic events	Events requiring the assistance of an external third party person
Rate of diabetic ketoacidosis (DKA)	Measured by self-report and confirmed through review of hospital records
Quality of Life (e.g. Fear of Hypoglycemia Survey)	As assessed using validated instruments (PedsQL and Insulin Treatment Satisfaction Questionnaire (ITSQ)).
Adverse Events	
Hypoglycemic events (clinically significant events)	See primary and secondary outcomes above. Insulin in any form is known to be associated with low blood sugars. Therefore, we are measuring this as a primary/secondary outcome...but it also may be considered an adverse event/safety event.
Severe hypoglycemic events (<54mg/dl by CGM) > 10%	In the case severe hypoglycemia exceeds 10% on any CGM sensor, the treating clinician will be notified.
Skin discomfort/irritation	Self-report
Skin infection	Self-report

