## 9.2 SAMPLE SIZE DETERMINATION

We estimated power using a bootstrap-resampling approach due to the expected non-standard distribution of the outcome variables (i.e. %time in serious hypoglycemia and %time-in-range). Using individual patient level CGM data collected from a pilot study involving more than 80 children with T1D in Uganda and Kenya (personal communication [name], University of Minnesota), we calculated a mean percent time $<54$  mg/dl of 5.8, standard deviation of 6.6, a maximum of 24. We next assumed a clinically meaningful 33% relative reduction in percent time-in-serious-hypoglycemia (e.g., from a median of 6% to 4%) since clinical guidelines recommend that patients and providers aim for <15 minutes per day (~1%) in hypoglycemia spent at <54 mg/dl. Therefore, in each simulated trial, the simulated patients in the usual-care arm had an outcome drawn from the “control” distribution; the simulated patients in the glargine arm had an outcome drawn from the control distribution multiplied by 0.67 (e.g. corresponding to a 33% relative reduction in time-in-serious-hypoglycemia).

To estimate the study power, we simulated outcomes for control-group (human insulin) and treatment-group (analogue insulin) at sample sizes ranging from 100 up to 400 patients and performed the planned primary analyses described above on the simulated datasets. The power to detect a treatment benefit of glargine insulin is thereby computed as the percentage of simulated trials with a p-value less than 0.025 favoring glargine on each of the respective coprimary outcomes. Since we have 2 coprimary outcomes, an alpha threshold of 0.025 is used for each analysis to control the overall trial-wide type 1 error probability at 0.05. Using this approach, an analytic sample size of 300 patients (150 per arm) would have 77.7% power to detect a treatment benefit corresponding to approximately a 33% relative reduction in time-in-serious-hypoglycemia. If the benefit is larger (e.g. 50% relative reduction) we will have over 99% power to detect a treatment benefit on the hypoglycemia endpoint.

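### The multiple-imputation sensitivity analysis is tied to baseline data and names no post-randomization predictor, although month-3 CGM and HbA1c are already scheduled

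*Combined protocol and SAP*

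**What the plan says.** Section 9.4.2 builds each co-primary outcome from the two sensors worn in months 6 to 7, one pooled value per participant. It analyses them by linear regression on arm, age, site and baseline CGM. For participants without an outcome it announces several sensitivity analyses. The first is "multiple imputation analysis, imputing the missing outcome data based on observed baseline data". The second is a win-ratio analysis that ranks death, discontinuation for an adverse event and other discontinuation below all completers, and ranks completers on time below 54 mg/dl.

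The paragraph of 9.4.2 on incomplete sensor data separately says "we will impute for missing data". It gives no model and does not say whether this is the same analysis.

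Section 3 schedules "one follow-up sensor starting 3 months after randomization". Section 8.2 lists "Mean HbA1c lab result at baseline, 3, 6, 9 and 12 months after randomization". The amendment history (10.4) records that the month-3 sensor was added on the DSMB's recommendation, so that earlier data would exist if participants were lost.

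On loss to follow-up, 9.4.2 leaves out of the primary analysis a participant who discontinues before any follow-up CGM, with the example "participant has no recorded CGM data at all during follow-up". It describes the 25% allowance as "participants that are lost shortly after randomization, before any CGM data have been collected".

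**The concern.** The plan itself recognises that discontinuation may reflect a poor clinical course. That course is seen after randomization, and the month-3 sensor and HbA1c are the scheduled measurements of it before the outcome window. An imputation restricted to baseline data ignores them.

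The primary model already conditions on age, site and baseline CGM. Imputing from the same information plus arm adds nothing to the complete-case fit. If dropout after month 3 depends on glycemia and does so differently by arm, both analyses carry the same error, and their agreement would look like robustness without having tested it. Other baseline variables listed in 9.4.5, such as HbA1c, C-peptide and diabetes duration, help only for dropout that depends on them.

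**Working it through.** **Inputs from the documents.** Time-in-range (TIR): SD 17, planned effect +10. Time below 54 mg/dl: mean 5.8, SD 6.6, glargine values multiplied by 0.67, so the effect is 0.33 × 5.8 = 1.914. Analysable N is 300, recruited N is 400, alpha is 0.025 per outcome (9.2, 9.4.2).

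**The plan's own figures.** 300 / (1 - 0.25) = 400, as stated. For time below 54, the average SD is √[(6.6² + (0.67 × 6.6)²)/2] = 5.62 and the standard error is 5.62 × √(2/150) = 0.649. The ratio is 1.914 / 0.649 = 2.95, and two-sided alpha 0.025 gives 76.1% power by normal approximation, against 77.7% stated from a bootstrap. The inputs are therefore read correctly; no stated number is disputed.

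**Why baseline imputation returns the complete-case result.** Let X hold the intercept, arm and primary covariates, and let b be the complete-case fit. Then X_obs′(Y_obs - X_obs b) = 0. Missing values are drawn around X_mis b, so on average X_mis′(Y_imp - X_mis b) = 0. Adding the two shows that b also solves the regression on the completed data. This holds whatever drives dropout.

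**Assumptions not in the documents.** Loss of 10% or 25%, all after month 3. Correlation of baseline with later values 0.4 to 0.6, and of month 3 with month 6-7 0.5 to 0.8. Log-odds of dropout 0.5 or 1.0 per SD of month-3 glycemia. Outcomes normal unless stated.

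**Large-sample bias in the TIR difference (truth +10; 800,000 simulated participants per cell).** Complete case and baseline imputation agree in every cell.

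| Dropout after month 3 | Bias, both methods |
|---|---|
| Same within-arm mechanism in both arms | -0.07 to +0.06 |
| One rule on absolute month-3 TIR, +10 already present at month 3 | -0.61 to -0.08 |
| Depends on TIR in the control arm only | -1.65 to -0.25 |
| Depends on TIR in the glargine arm only | +0.28 to +1.57 |

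With month-3 TIR observed for every dropout and added to the imputation, the remaining bias is within 0.09. A separate re-run of this grid gave the same pattern.

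**Finite-sample check.** Full multiple imputation, N = 400, 20% loss, correlations 0.5 and 0.65, log-odds 1.0, control-arm dependence. Mean TIR effects were 8.88 (complete case), 8.87 (baseline imputation) and 10.06 (with month 3). By hand, the partial coefficient of month 3 given baseline is (0.65 - 0.5 × 0.5)/(1 - 0.5²) = 0.533, or 0.533 × 17 = 9.07 points per SD. The bias of 1.12 thus needs control completers to sit only 1.12 / 9.07 = 0.12 SD above what baseline predicts at month 3.

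**Scale.** At correlations 0.6 and 0.8 with 25% loss, the standard error of the TIR effect is about 1.57. The largest one-arm bias, 1.65, is about one standard error.

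**Time below 54 mg/dl.** A normal model with mean 5.8 and SD 6.6 puts Φ(-5.8/6.6) = 19% of values below zero, so the skewed run is the relevant one (gamma with those moments, glargine × 0.67, truth -1.91). Bias was +0.06 to +0.39 for a shared within-arm mechanism and +0.11 to +0.63 for one absolute rule. For arm-specific dropout it was +0.15 to +0.87 (control only) and -0.43 to -0.09 (glargine only). With month 3 it was within 0.04.

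**Limits of the remedy.** Month-3 data remove about half (46-60%) of the bias if half the dropouts have them, and 15-51% if arm-specific dropout follows the unobserved month-6 value. They remove none for losses before month 3.

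**The case against.** The strongest reply is that the affected group may be very small. The 25% allowance is placed before any CGM data, where month-3 values do not exist, and no section quantifies later loss. This stands: with few late losses the gain is near zero.

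Second, the larger biases need dropout that depends on glycemia differently by arm, and the documents give no evidence of it. Several features weaken such a link. CGM readings are hidden from participants (4.1). Stopping the assigned insulin is not leaving the study (7.1). The plan's examples of missing data are sensors that fall off or are lost, with some replacement allowed. This stands too, so the one-arm figures are illustrations. The open-label design makes arm-specific dropout possible but does not show it.

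Third, the imputation is one of several checks, and the win-ratio analysis addresses death and discontinuation directly. That is a partial answer. The win-ratio uses no month-3 data and ranks completers on time below 54 only, so for TIR the imputation carries the load.

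Fourth, baseline data may include more than the primary covariates, and the other mention of imputation is not restricted to baseline. Both are correct. Richer baseline variables still do not record the course after randomization, and an imputation with no stated model cannot be relied on to use month 3.

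A reader might also infer that arm is left out of the imputation. The documents do not say so; listing it would simply settle the question.

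**Conclusion.** The point holds as a free improvement to one sensitivity analysis. As worded, that analysis is likely to repeat the complete-case result and so gives little information about dropout related to glycemia after randomization, although suitable data are scheduled and the month-3 sensor was added with participant loss in mind.

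Under the stated assumptions, the TIR error that it would miss is about 0 for a shared within-arm mechanism and up to about -0.6 points for one absolute month-3 rule. It is about 0.3 to 1.7 points in either direction for dependence in one arm only. For skewed time below 54, some bias (+0.06 to +0.39 against -1.91) remains even with a shared mechanism. All of these figures rest on assumed correlations, dropout mechanisms and 10-25% loss after month 3.

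A reader might go further and infer that the primary analysis is wrong or that the trial's conclusion is at risk. The documents do not support that. The primary analysis does not use this imputation, late loss is not quantified, and at the planned +10 the TIR conclusion would not change, only its estimated size.

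One related ambiguity is open. The synopsis speaks of 3-6 months, while 8.2 and 9.4.2 define the outcome from the sensors starting at month 6. The loss-to-follow-up text excludes only those with no follow-up CGM of any kind. A participant with month-3 but no month 6-7 CGM therefore has no stated handling.

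**What to change.** - For both co-primaries, specify the imputation model: arm, age, site, baseline time below 54 and TIR, month-3 time below 54 and TIR, HbA1c at months 3 and 6, and later scheduled CGM and HbA1c where available.
- Name a method suited to a skewed, bounded time below 54 mg/dl.
- State that the analysis still assumes missing at random.
- Report missing month 6-7 CGM by arm and by whether month-3 data exist, so that readers can see how far this check reaches.
- Ask the sponsor to reconcile the synopsis, 8.2 and 9.4.2 on participants with month-3 but no month 6-7 CGM. Sections 8.2 and 9.4.2 point to month 6-7 as the outcome, with such participants entering through the imputation, but the sponsor should confirm it.
- Say whether the two mentions of imputation in 9.4.2 are one analysis.

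The cost is a few sentences of SAP text and a few lines of code. No new data are needed. The primary regression stays as it is; what remains for the sponsor to confirm is how month-3-only participants are handled.

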## 9 STATISTICAL CONSIDERATIONS

### 9.1 STATISTICAL HYPOTHESES

Null hypothesis: % Time-in-serious hypoglycemia and % Time in Range (TIR) in the insulin glargine group is the same as % Time-in-serious hypoglycemia and % TIR in the control group (usual care with human insulin).

Alternative hypothesis: % Time-in-serious hypoglycemia or % TIR in the insulin glargine group is different than in the control group (usual care with human insulin).

Since this trial has 2 coprimary outcomes, a win on either outcome will be considered to be a positive trial. For example, if insulin glargine “wins” ( $p<0.025$  for benefit) on either the Time-in-serious hypoglycemia OR TIR outcome, it’s considered a positive trial for analogue insulin.

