#### 9.4.3 ANALYSIS OF THE SECONDARY ENDPOINT(S)

The secondary outcomes are: Time-in-hypoglycemia (<70mg/dl), time-above-range (either >180mg/dl or >250mg/dl), and number nocturnal hypoglycemic events (1200-0600h). We will also measure and compare overall glycemic control (HbA1c), the rate of severe hypoglycemic events (requiring the external assistance of another party), and the rate of symptomatic hypoglycemic events reported by clinical history, rate of diabetic ketoacidosis (measured by self-report and confirmed through review of hospital records) and overall mortality (all cause death).

We will also measure and compare quality of life using validated tools (PedsQL v3 and Insulin Treatment Satisfaction Questionnaire) at baseline and at 6 and 12 months after randomization. A minimum clinically important difference in QoL scores will be determined *a priori*. The primary treatment comparison for QoL will be made between the two treatment arms at 6 months after randomization.

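### The win-ratio sensitivity analysis is meant to cover a time-in-range benefit, but time-in-range is in none of its tiers

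*Combined protocol and SAP*

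**What the plan says.** Section 9.4.2 gives two sensitivity analyses for participants who discontinue. The first is multiple imputation, "imputing the missing outcome data based on observed baseline data". The second is a single win ratio. Deaths rank worst, then discontinuations for an adverse event, then discontinuations without a known adverse event. Below these, "participants that return complete CGM data during the intensive follow-up period are ranked according to their % time-in-serious-hypoglycemia", with more time below 54 mg/dl counted as worse. The plan describes the result as "including death, discontinuation, and hypoglycemia into a single composite outcome measure".

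The same paragraph states what the analysis is for: to check that "any observed benefits on a time-in-serious-hypoglycemia outcome or the time-in-range outcome are not offset" or explained by more deaths or discontinuations, which it places in the other arm. Both coprimary outcomes are named in that purpose.

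Section 9.1 sets the success rule: "a win on either outcome will be considered to be a positive trial".

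**The concern.** The purpose names two glycemic outcomes and the ranking reads one. An analysis that never uses TIR cannot say whether a TIR gain is outweighed by deaths or dropouts.

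This matters most if the trial succeeds on TIR alone. That route is realistic on the plan's own figures: at N=300 the stated power is 77.7% for a 33% reduction in time below 54 mg/dl and more than 99.9% for a 10-point TIR gain (section 9.2). If both effects are true, about 22% of such trials (100 − 77.7) would miss on hypoglycemia, and nearly all of those would still win on TIR. If such a win came with more dropout on glargine, the written win ratio would show the dropout but give the TIR gain no credit.

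No other planned analysis fills this gap. Multiple imputation can be applied to TIR, but it does not score discontinuation as a bad outcome. The mortality comparison in section 9.4.3 stands on its own.

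**Working it through.** **Reading the text.** The mismatch is settled by setting the passages of section 9.4.2 side by side.

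| Element | Time below 54 mg/dl | TIR |
|---|---|---|
| Coprimary outcome | yes | yes |
| Named in the win ratio's purpose | yes | yes |
| Present in a win-ratio tier | yes (last tier) | no |
| Named in the plan's description of the composite | yes | no |

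Section 9.4.2 also says that the TIR analysis mirrors the hypoglycemia analysis, but that sentence goes on to specify the linear regression model. It does not extend to the win ratio.

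**Inputs for an illustration.** The plan states no figure for the win ratio. From section 9.2: TIR effect +10 points, SD 17. Assumed here, not in the documents: the dropout rates, no effect on time below 54 mg/dl, normal TIR, and all dropouts pooled in one tier.

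The TIR inputs are read as the plan uses them. With 150 per arm and two-sided alpha 0.025, the standard error is 17 × √(2/150) = 1.963, z = 10/1.963 = 5.09, and power = Φ(5.09 − 2.24) = 99.8%, against the stated >99.9%. At N=200 and N=250 the same method gives 97.2% and 99.2%, against 97.5% and 99.5%.

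**Formula.** Let dG and dC be dropout on glargine and control, and p the chance that a glargine completer beats a control completer on the last tier.

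- Wins = (1 − dG)·dC + (1 − dG)(1 − dC)·p
- Losses = dG·(1 − dC) + (1 − dG)(1 − dC)·(1 − p)
- Pairs in which both dropped out are ties and are ignored.

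As written, with no effect on time below 54, p = 0.5. With TIR as the last tier, p = Φ(10/(17√2)) = Φ(0.416) = 0.661.

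**Example, 20% v 10%.**

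- As written: wins 0.08 + 0.36 = 0.440; losses 0.18 + 0.36 = 0.540; ratio 0.81.
- TIR tier: wins 0.08 + 0.72 × 0.661 = 0.556; losses 0.18 + 0.72 × 0.339 = 0.424; ratio 1.31.

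| Dropout, glargine v control | As written | TIR as last tier |
|---|---|---|
| 15% v 10% | 0.90 | 1.50 |
| 20% v 10% | 0.81 | 1.31 |
| 25% v 10% | 0.73 | 1.15 |

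Average dropout in the last row is (25 + 10)/2 = 17.5%, within the plan's 25% allowance.

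**Break-even.** With a TIR tier and dC = 10%, wins equal losses when dG = (0.1 + 0.9 × 0.322)/(1 + 0.9 × 0.322) = 0.3898/1.2898 = 30.2%. Only there is the TIR gain fully offset. The written ratio is below 1 at any excess dropout on glargine, given no effect on time below 54.

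**Simulation.** With 200 per arm, 20% v 10% dropout and no effect on time below 54, the written win ratio averaged about 0.81 both with a 10-point TIR gain and with none. With a TIR tier and the 10-point gain it averaged 1.31. The written analysis does not respond to TIR.

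**The case against.** The case on the other side has four parts.

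1. *Most of the purpose is already served.* The three upper tiers show an imbalance in deaths or discontinuations whatever the last tier is. Multiple imputation is not limited to one endpoint, and mortality is compared separately. This stands, and it is why the point is minor. It leaves open whether a TIR gain is offset.

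2. *The scenario is chosen.* It sets the effect on time below 54 to zero, whereas the plan assumes a 33% reduction. With that reduction (gamma or lognormal, mean 5.8, SD 6.6), the written ratio is 1.17 to 1.32 at 15% v 10% and 1.04 to 1.17 at 20% v 10%. This stands as a limit on the figures. In those cases the ratio exceeds 1 because of the hypoglycemia effect; the TIR gain still earns nothing.

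3. *The direction is ambiguous.* The purpose sentence places the excess deaths or discontinuations in the other arm. Read literally, that is the arm without the benefit. At 10% on glargine and 20% on control, with no effect on time below 54, the written ratio is 0.54/0.44 = 1.23. The ambiguity is real, though the idea of a benefit being offset fits excess loss in the benefiting arm better. On either reading TIR is not weighed.

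4. *The composite is labelled correctly, and 0.81 is the right answer for it.* This is true: 0.81 and 1.31 describe different composites, and neither is a miscalculation. The fault is that the composite as defined cannot serve the purpose stated for TIR. Narrowing that purpose would be enough for consistency.

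**Conclusion.** The concern holds. The win ratio in section 9.4.2 claims to check a TIR benefit and contains no TIR component, so its result is the same with or without a TIR gain. In the illustration, the choice of last tier moves the ratio from 0.81 to 1.31 at 20% v 10% dropout. Those sizes rest on assumed dropout rates, no effect on time below 54 mg/dl and normally distributed TIR; the mismatch itself rests only on the text.

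The consequence is limited. This is a sensitivity analysis, and an imbalance in deaths or dropouts would still be visible. It would matter chiefly for interpreting a trial that is positive on TIR alone.

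**What to change.** Pre-specify a second win ratio with the same three upper tiers and TIR as the last tier, lower values being worse. The cost is a sentence or two in section 9.4.2 and one extra run of the same code. Failing that, limit the purpose sentence to time-in-serious-hypoglycemia, which is a wording change only. Either way, reword the reference to the other arm so that the direction of the feared imbalance is clear.

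Three smaller gaps in the ranking can be closed in the same edit:

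- Completeness of CGM data in the last tier is not defined. The primary analysis uses all available sensor data; the win ratio could likewise rank participants still on study on any month 6–7 data.
- Participants still on study with no month 6–7 CGM have no stated rank. Section 9.4.2 itself expects some sensors to be lost before download.
- State whether a participant who discontinues after giving month 6–7 CGM belongs in a discontinuation tier. The ordering suggests so, but the plan does not say it.
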